Phendimetrazine (PHEN), a Schedule III medication under the Controlled Substance Act, is indicated for treating obesity. After oral administration, PHEN is converted to phenmetrazine, which is largely responsible for its behavioral and neuropharmacological effects. Consistent with the notion that compounds with intermediate 5-HT/DA release ratios selectively attenuate the reinforcing effects of COC, phenmetrazine (5-HT/DA ratio = 37) completely eliminated COC-maintained responding in monkeys. Recent research with PHEN has also shown that the parent compound reduces COC self-administration. Moreover, PHEN does not maintain self-administration and produces only limited positive subjective effects compared to d-amphetamine in COC users, which suggests that its abuse potential is low. Although PHEN has yet to be tested as a potential pharmacotherapy for COC dependence in human laboratory experiments or clinical trials to our knowledge, the results of extant preclinical experiments suggest it is a viable option.

In an ongoing study, we have demonstrated that COC can be safely administered to patients maintained on 70, 140 and 210 mg PHEN/day. Whether PHEN attenuates the reinforcing effects of COC, the best predictor for treatment efficacy (Comer et al., 2008; Haney and Spearman, 2008), remains to be determined. **The specific aim of this study is to demonstrate that PHEN maintenance reduces the reinforcing effects of intranasal COC.** To accomplish this aim, we will conduct an experiment in which non-treatment seeking COC-using participants (N=36) will be maintained on doses of PHEN (0 and 210 mg/day [target dose, dose will be titrated up as described below]). The reinforcing and other behavioral effects of intranasal COC (0 [placebo], 20, 40 and 80 mg) will be determined after 7 days of maintenance on the target PHEN dose (i.e., 210 mg/day). In order to monitor the safety of the drug combinations, cardiovascular measures will be taken routinely throughout experimental sessions and subjects will complete a daily side effect scale with nursing staff. We hypothesize that PHEN will attenuate the reinforcing effects of COC, as well as other abuse-related effects of COC (i.e., positive subjective effects). We also hypothesize that COC will be well tolerated during active PHEN maintenance.

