## **2. OBJECTIVES**

The primary objective of this study is to determine the reinforcing effects of COC during maintenance on PHEN. We will also include a battery of subjective, performance and cardiovascular measures to more fully characterize the influence of PHEN maintenance on the effects of COC.

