Subjects will be excluded from further research participation if at any time during the experimental sessions COC increases heart rate above 130 bpm, systolic pressure above 180 mmHg, diastolic pressure above 120 mmHg or if clinically significant and/or prolonged ECG abnormalities are noted. Subjects will remain seated for the duration of the experimental session. Between the sampling and self-administration phases, subjects will be allowed to eat a standard hospital lunch but will not be allowed to smoke. No experimental activities will be scheduled for the remainder of the day after a self-administration session, but subjects will receive their appropriate maintenance medication at 1900 hours. Subjects will be free to engage in recreational activities (e.g., watch television, read, listen to music, arts and crafts, play video or board games). Research subjects will be required to be in bed with the lights out by 2300 hours.

Time	Table 2-Daily Activities for Maintenance Days
0700	Patient awakened. Vital signs recorded. Medication administered if vitals are within range and no indication of sedation or withdrawal. Subject eats breakfast.
1200	Lunch is served.
1300	UKU completed.
1900	Dinner is served. Vital signs recorded. Medication administered if vitals are within range and no indication of sedation or withdrawal.
2300	Lights out.

Time	Table 3-Daily Activities for Experimental Days
0700	Patient awakened. Vital signs recorded. Medication administered if vitals are within range and no indication of sedation or withdrawal. Subject eats breakfast.
0900	Vital signs recorded. Computerized tasks completed. ECG monitoring begins.
0930	Vital signs recorded. 0 [placebo], 20, 40 or 80 mg intranasal COC administered if vitals are within range. Measures completed 0, 15, 30, 45 and 60 minutes after drug administration.
1030	Sampling phase ends.
1200	Lunch is served.
1300	UKU is completed.
1330	Vital signs recorded. Computerized tasks completed (including progressive-ratio task). ECG

	monitoring begins.
1430	Vital signs recorded. Portion of intranasal dose earned is administered if vitals are within range. Measures completed 0, 15, 30, 45 and 60 minutes after drug administration
1530	Session ends. Remainder of daily activities identical to those listed in Table 2.

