**Vital Signs.** Heart rate, blood pressure, oral temperature and heart rhythmicity (via ECG) will be recorded using a Dinamap digital monitor (Critikon, Pro 1000, Tampa, FL). These measures will be completed at as described in the tables above. Telemetry-certified nurses will interpret the results of the ECG with instructions to contact Drs. [name] or [name] regarding abnormalities.

**Performance Task.** Psychomotor performance will be assessed at the same time as subjective drug-effects during all sessions with a computerized version of the Digit-Symbol-Substitution Test (DSST) (McLeod et al., 1982). In this procedure, the subject uses a numeric keypad to enter a geometric pattern displayed on a video screen. Subjects will have 90 seconds to enter as many geometric patterns as possible. The dependent measures are the number of geometric patterns the subject attempted to enter and the number of patterns entered correctly. This task will be completed immediately following the subjective questionnaires.

**Drug Dose and Administration.** All drugs will be administered under double-blind conditions and under medical supervision. COC doses will be given in random order. PHEN doses will be given in counterbalanced order across subjects. Doses of COC HCl will be prepared by weighing out the appropriate amount of powdered COC. The powder will then be mixed with lactose monohydrate powder, N.F. to make a total of 100 mg powder. Placebo will be prepared in an identical fashion, but will contain only lactose monohydrate powder. Doses of COC will be prepared individually for each subject. Doses of 0 [placebo], 20, 40 and 80 mg intranasal COC will be placed into individual glass vials labeled for each subject for each sampling session. Doses of PHEN (0, 35, 70 and 105 mg, administered two times daily) will be prepared by over-encapsulating commercially available tablets in a size 0 capsule. The capsule will then be loose filled with cornstarch. Placebo capsules will be prepared in an identical fashion, but will contain only cornstarch.

**Data Analysis.** Data will be analyzed as raw scores. Statistical significance refers to  $p \leq 0.05$ .

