Progressive-ratio data (i.e., break point, number of COC doses earned) will be analyzed with two-factor mixed-model ANOVA with COC (within-subject variable; 0 [placebo], 20, 40 and 80 mg), and PHEN (within-subject variable; 0 and 210 mg/day) as the factors. A significant attenuation (i.e., rightward shift in the dose response) of the effects of COC will be inferred if the main effect of PHEN or the interaction of COC and PHEN attains statistical significance in the ANOVA. If the COC-PHEN interaction attains statistical significance, the mean square error term will be used to conduct Tukey's HSD *post-hoc* test to make appropriate pair-wise comparisons between means. Peak-effect and AUC data for the cardiovascular, performance and subjective effects measures obtained during the sampling phase will be analyzed in a similar fashion. Cardiovascular, performance and subjective effects data from the self-administration phase will not be analyzed because participants will likely ingest varying amounts of COC making these data difficult to interpret.

The primary outcome measures for this study are the break point and number of COC doses earned on the progressive-ratio procedure in subjects maintained on active PHEN or placebo. Considering the complete within-subject design, number of dose levels of each drug (i.e., two PHEN conditions and four doses of intranasal COC) enrolling 36 subjects will provide adequate power to detect an effect size ( $d$ ) of at least 0.44 for attenuation of the reinforcing effects of COC as a function of maintenance on PHEN and placebo ( $\text{power} = 0.80$ ,  $\alpha = 0.05$ , G\*Power). We used the results of a previous study conducted in our laboratory to determine an appropriate sample size for the present experiment ([name] et al., 2010). That study demonstrated that d-amphetamine maintenance decreased the reinforcing effects of COC with an estimated effect size ( $d$ ) of approximately 0.46.

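### For the sampling-phase measures, a PHEN main effect alone is read as attenuation of COC's effects, so PHEN's own standing effect can satisfy the rule

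*Combined protocol and SAP*

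**What the plan says.** The rule is in Section 7, Data Analysis. Attenuation, which the plan glosses as the dose-response curve moving to the right, "of the effects of COC will be inferred if the main effect of PHEN or the interaction of COC and PHEN attains statistical significance". Either test is enough and no direction is required. Tukey comparisons follow only if the interaction is significant.

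The next step extends the analysis: "Peak-effect and AUC data for the cardiovascular, performance and subjective effects measures obtained during the sampling phase will be analyzed in a similar fashion". No other inference rule is given for these measures. On scale, the plan says: "Data will be analyzed as raw scores". A pre-dose battery is collected, but the analysis gives it no role.

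On timing, the 0700 row of Table 3 reads: "Patient awakened. Vital signs recorded. Medication administered if vitals are within range and no indication of sedation or withdrawal". Pre-dose measures follow at 0900 and the sampling dose of COC at 0930.

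On purpose, Section 2 includes a "battery of subjective, performance and cardiovascular measures to more fully characterize the influence of PHEN maintenance on the effects of COC". Section 1 states: "We hypothesize that PHEN will attenuate the reinforcing effects of COC, as well as other abuse-related effects of COC", and gives positive subjective effects as the example. For vital signs, Section 1 has a safety aim: "In order to monitor the safety of the drug combinations, cardiovascular measures will be taken routinely".

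**The concern.** The question for these measures is whether PHEN makes the response to COC smaller. A PHEN main effect does not answer it. It compares all PHEN sessions with all placebo sessions, including the sessions with no COC. If PHEN by itself moves a measure, every session on PHEN moves with it and the main effect can reach significance with COC's effect untouched.

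A standing PHEN effect is possible on the documents' own account. Section 9 lists heart-rate and blood-pressure changes, nervousness, restlessness and performance impairment together as side effects of the two drugs. It gives no sizes and no direction for heart rate, and it calls side effects unlikely at these doses. So the documents show that a shift can occur, not that it will.

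At stake is a reported statement that PHEN attenuates a subjective, performance or cardiovascular effect of COC when the result is PHEN's own effect. The exposure is greatest for vital signs and for the Adjectives Rating Scale items on how the subject feels at the moment. It is smaller for Drug Effect Questionnaire items, which ask about the drug. For vital signs, where only tolerability is hypothesized, the harm is a mislabelled result; the raw PHEN effect remains useful for safety.

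**Working it through.** **1. The plan's own figure.** The plan says that "enrolling 36 subjects will provide adequate power to detect an effect size" of at least 0.44 with power 0.80 and alpha 0.05. A paired t-test with N = 36 and a standardized difference of 0.44 has power 0.728 two-sided and 0.827 one-sided. The two-measurement repeated-measures form gives 0.80 two-sided if the within-subject correlation is about 0.58. Sidedness, correlation and the SD behind d are not stated, so the figure cannot be settled. The point does not depend on it; 0.44 serves below only as a yardstick.

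**2. The logic.** Let the mean under PHEN condition p (0 or 1) and COC dose c be μ(p,c) = m + g(c) + p·s, with g(0) = 0. COC's response g is the same in both conditions, and s is PHEN's standing shift.

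- Main effect: (1/4) Σ over c of [μ(1,c) − μ(0,c)] = s.
- COC response on PHEN minus on placebo, at 80 mg: [μ(1,80) − μ(1,0)] − [μ(0,80) − μ(0,0)] = g(80) − g(80) = 0.

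The main effect equals PHEN's own shift although nothing about COC has changed. To see the confusion in numbers, assume COC heart-rate rises of 0/3/6/10 bpm. Halving them with s = 0 gives a main effect of −(0 + 3 + 6 + 10)/(4 × 2) = −2.375 bpm. A standing shift of −2.375 bpm with COC unchanged gives the same main effect. The 80 mg minus 0 mg contrast separates them: 5 − 10 = −5 bpm against 0.

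**3. Scale-free size.** Noncentral t, 35 df, noncentrality √36 × dz = 6·dz, two-sided 0.05. Here dz is the shift divided by the SD of the subject-level PHEN-minus-placebo difference (assumed values):

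| dz | noncentrality | main effect significant |
|---|---|---|
| 0.30 | 1.80 | 0.417 |
| 0.44 | 2.64 | 0.728 |
| 0.50 | 3.00 | 0.831 |

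**4. Heart-rate simulation.** All SDs are assumed: subject 10, period 4, session 3, reading 3 bpm. COC rises are 0/3/6/10 bpm, unchanged by PHEN; five readings per session; 4,000 trials per scenario. For the raw peak:

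- Shift +2/+3/+5 bpm: main effect significant in 0.466/0.809/0.997.
- Shift −2/−3/−5 bpm: significant lowering in 0.472/0.801/0.996.
- AUC at +3 or −3 bpm: 0.816.
- Interaction: 0.043 to 0.054. Dose-trend-by-PHEN contrast showing lowering: 0.024 to 0.030.

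Main effect at +3 bpm as the assumed SDs vary:

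| Session SD | Period SD 2 | 4 | 6 | 8 |
|---|---|---|---|---|
| 3 | 0.996 | 0.801 | 0.501 | 0.328 |
| 5 | 0.957 | 0.729 | 0.469 | 0.300 |
| 8 | 0.769 | 0.580 | 0.403 | 0.281 |

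False lowering at −3 bpm runs from 0.997 to 0.271 over the same range.

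**5. A 0–4 rating item.** Assumed latent SDs: subject 0.5; period, session and reading 0.3. Scores are rounded and clipped; COC's latent response is unchanged; the latent PHEN shift is −0.3:

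| Mean peak at COC 0 mg | main-effect lowering | interaction | trend lowering |
|---|---|---|---|
| 1.35 (mid-scale) | 0.901 | about 0.05 | about 0.03 |
| 0.22 (near floor) | 0.835 | 0.193 | 0.242 |

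Near the floor, clipping compresses the low-dose scores and turns an additive shift into an apparent interaction.

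**6. No PHEN effect at all.** If the two tests are independent, the either/or rule fires in 1 − 0.95² = 0.0975 of trials per measure (simulated 0.093 to 0.096).

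**The case against.** - **Reach of the rule.** The rule sits among sentences on the progressive-ratio data, and the extension clearly carries over the ANOVA but only by inference the rule. That is fair. But the rule speaks of COC's effects in general, and if it does not apply, these measures have no inference rule and one must be written.
- **Direction.** The rightward-shift gloss makes it strained to call a PHEN-induced rise attenuation, so the upward results deserve less weight. This stands. The gloss does not rescue the rule, though: a parallel downward shift, already present at COC 0 mg, is not a rightward shift either.
- **Plausibility of a downward shift.** PHEN's listed effects include nervousness and restlessness, which would raise those items, and Section 1 credits it with limited positive effects. Performance impairment is the clearest documented downward route and was not modelled. Section 9 also says side effects may be larger with the combination, which is more than a constant shift. These limit how likely the error is, not whether the rule permits it.
- **Baseline.** If peak and AUC were computed from the pre-dose value, most of a standing shift would cancel. The plan specifies raw scores and mentions no subtraction.
- **Visibility.** COC 0 mg is tested under both PHEN conditions, so a reader could see the shift in reported means. But no such look is planned when only the main effect is significant.
- **Primary outcomes.** The same rule is written for break point and doses earned. They are left outside this point as a matter of scope; no calculation here tests them.

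**Conclusion.** The concern holds. As written, a PHEN main effect is sufficient to infer attenuation of COC's effects on the sampling-phase measures, and a standing PHEN effect can supply that main effect while the response to COC is unchanged. This follows from the averaging over COC 0 mg and needs no assumed figure. If attenuation is read as lowering only, it still holds for a downward shift present at COC 0 mg.

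The size is illustrative, because the documents give no SDs, shifts or COC responses for these measures. Across the assumed heart-rate SDs, a 3 bpm shift triggers the main effect in anything from over 99% to about 27% of trials.

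These are not primary outcomes, so the correction should be made but does not bear on the main result. Confidence is high in the logic and limited in the magnitude.

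**What to change.** For the sampling-phase measures:

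- Infer attenuation only from a COC-by-PHEN interaction, or one pre-stated contrast, that shows a smaller COC response on PHEN. State the direction for each measure. The dose-trend-by-PHEN contrast, or 80 mg minus 0 mg, keeps more power than the mean of the active doses minus 0 mg.
- Report the PHEN main effect, and PHEN's effect on the 0900 pre-dose values, separately as PHEN's own effect.
- Keep raw peaks as the cardiovascular safety summary.
- For 0–4 items near the floor at COC 0 mg, show the COC 0 mg scores and read any interaction with caution.

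The cost is plan wording and minor programming, with no new data. There can also be a cost in power. With the heart-rate assumptions above, no standing shift, and COC's response halved by PHEN (6,000 trials):

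| Test | Session SD 3 | 5 | 8 |
|---|---|---|---|
| Current either/or rule | 0.936 | 0.710 | 0.461 |
| Dose-trend contrast | 0.953 | 0.680 | 0.359 |
| 80 mg minus 0 mg | 0.940 | 0.646 | 0.331 |
| 3-df interaction | 0.885 | 0.525 | 0.235 |
| Mean active minus 0 mg | 0.739 | 0.418 | 0.199 |

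For a 30% reduction, the rule gives 0.553/0.351/0.242 and the trend contrast 0.594/0.315/0.170. Absolute power depends on the assumed time course of COC's effect.

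Part of the rule's rate is its null firing rate: about 10% as written, or about 7% if only the main effect must be a lowering (1 − 0.975 × 0.95 = 0.074, the interaction staying non-directional). The directional trend fires in about 2.4%; because it is directional throughout, the 7% and 2.4% are not strictly like for like.

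Two limits remain. Near the floor of a rating item the change reduces false attenuation but does not remove it. And a parallel downward shift on PHEN would no longer count as attenuation, which the team should accept explicitly.

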## **17. DATA AND SAFETY MONITORING**

### *Data Monitoring Plan*

Data will be collected using a computerized data collection and management system wherever possible. This system automates the collection of data, which ensures the accuracy and completeness of data collection. The data are stored in a unique file on the hard drive of the computer and are printed after all the tasks are completed. In all instances, the data files do not contain the name of the subject, but instead, each subject is identified by a unique four-digit number. A computer file linking the unique number with the subject's name will be kept on a stand-alone, password-protected computer. All data requiring hand entry (e.g., cardiovascular measures) will be entered by two separate staff members and comparison macros will be run to ensure accuracy. Data files for experimental tasks and physiological measures from each experimental session will be manipulated and combined into a single electronic spreadsheet for each subject by one of the investigators. Data for all subjects will then be combined into a single electronic spreadsheet and separated by experimental measure for statistical analysis using SPSS (IBM, Armonk, NY).

In this protocol the primary outcome measure will be the influence of PHEN maintenance on the reinforcing effects of COC. The alpha level will be set at 5%.

As noted above, wherever possible, data are collected using an automated computer system, which increases the accuracy and completeness of data collection and ensures the validity and integrity of the data. The initial data manipulation described above will be conducted twice and compared. The quality of manipulated data and data analyses will be monitored by random inspection by the PI and/or Co-Investigators.

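### The attenuation rule checks neither the direction of the PHEN effect nor which COC doses changed, so any significant interaction, including one from a change at 0 mg alone, satisfies it

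*Combined protocol and SAP*

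**What the plan says.** The specific aim in section 1 is to "demonstrate that PHEN maintenance reduces the reinforcing effects of intranasal COC". The analysis is in section 7, Data Analysis: "Progressive-ratio data (i.e., break point, number of COC doses earned) will be analyzed with two-factor mixed-model ANOVA with COC" at 0, 20, 40 and 80 mg and PHEN at 0 and 210 mg/day, both within-subject. The decision rule opens "A significant attenuation (i.e., rightward shift in the dose response) of the effects of COC will be inferred if", and its whole condition is that attenuation "will be inferred if the main effect of PHEN or the interaction of COC and PHEN attains statistical significance in the ANOVA".

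A follow-up is planned for one case only: "If the COC-PHEN interaction attains statistical significance, the mean square error term will be used to conduct" Tukey's HSD for pairwise comparisons, which are not listed. No follow-up is given for a main effect alone.

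The threshold is p of at most 0.05 per test. Section 17, Data Monitoring Plan, adds "The alpha level will be set at 5" percent. On outcomes, section 7 says "The primary outcome measures for this study are the break point and number of COC doses earned".

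**The concern.** This is the only stated rule for deciding whether the aim is met, and its condition is weaker than its conclusion. An F test ignores sign. The 0 mg level enters both the PHEN main effect and the interaction, so a change in choosing lactose powder over money can trigger either. The Tukey result would describe an interaction but does not feed back into the inference, and nothing says which interaction pattern counts as attenuation.

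A fall at 0 mg with cocaine choice unchanged is not attenuation of cocaine's effects. A rise at 0 mg with cocaine choice unchanged flattens the dose-response curve and could be read as attenuation. If the rule does not settle such cases, they will be settled after the data are seen.

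**Working it through.** **What needs no assumptions.** Suppose PHEN changes choice by an amount c at 0 mg and not at 20, 40 or 80 mg. The PHEN main effect averages four doses, so it equals c/4. The interaction deviations are c - c/4 = 3c/4 at 0 mg and -c/4 at each active dose. Both tests therefore respond to a change at placebo alone, whatever the sign of c.

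**Null rate, literal reading.** The plan gives no error rate for the either/or rule, only 0.05 per test. With separate within-subject error terms the two tests are approximately independent: 1 - (1 - 0.05)^2 = 1 - 0.9025 = 9.75% per outcome.

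**Simulation.** From the plan: 36 subjects, a 2 x 4 within-subject layout, and 10 forced choices per session. Everything else is assumed, because the documents give no choice profiles or variances:
- Logit means at 0/20/40/80 mg: A (-2.5, -1, 0, 1), B (-1.5, -0.5, 0.5, 1.5), C (-1, 0.5, 1, 1.5), D (-3, -2, -1, 0).
- Logit SDs: subject 1.2, subject x PHEN 0.5 per condition, subject x COC 0.6, residual 0.5.
- Outcome: doses earned. Main effect F(1,35); interaction F(3,105); Tukey with the interaction mean square, 8 means, 105 df, critical q 4.37.

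Share of trials declared attenuation, range over the four profiles:

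| Assumed PHEN effect (logit) | Rule as written | Same, and overall PHEN mean lower | Proposed rule |
|---|---|---|---|
| None | 9.7-9.8% | 4.8-5.0% | about 3% |
| +0.5 at all active doses | 69-75% | near 0% | 0% |
| +1 at 0 mg only | 57-94% | 5-10% | under 2% |
| -1 at 0 mg only | 24-85% | 16-78% | 7-10% |
| -0.5 at all active doses | 72-76% | 72-75% | 65-70% |
| -1 at 80 mg only | 91-96% | not tabulated | 83-93% |

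A second model, with normal PHEN-minus-placebo differences that are independent across doses, gives the same picture. Under no effect the rule as written fires in 9.6% of trials. A standardised increase of 0.44 on the four-dose mean meets it in 74.2%, a decrease of the same size in 74.0%. A change at 0 mg only, of 0.44 to 0.88 SD, meets it in 58-99%.

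**Error terms.** The plan does not name them. With one pooled term and the same variances, the literal null rate is 7.4-9.3%. If the assumed subject x PHEN SD runs from 0 to 1.0, a pooled term gives 2.2-21.6%, while separate terms stay at 9.2-10.3%.

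**Two primary outcomes.** Under Self-Administration Phase, all 10 choices are forced, the first ratio is 400, and each selection of an option adds 100 to it. For one or more drug doses the break point is thus 300 + 100 x doses earned: 400 for one dose, 1300 for ten. The two outcomes differ only through the score for zero doses, which is not stated. Under the literal rule the second primary adds 0 points of error if zero doses are scored 300, and 2.9-3.7 points if scored 0.

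**The case against.** The strongest reply is that nobody would report an increase as attenuation. The rule's own sentence equates attenuation with a rightward shift, the aim speaks of a reduction, the prior study behind the sample size showed a decrease, and the sign would be visible in the means. This stands. A reader might infer that the plan would accept an increase in cocaine taking as success. The literal criterion permits it, but the surrounding text does not support it as the plan's meaning.

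A reader might also infer that the trial runs at nearly double its stated alpha. That stands only on the literal reading: about half of the 9.75% are trials with a higher PHEN mean, and reading the sign returns the rate to about 5%. It is not a separate inflation. Nor do two primaries double the error, since they are almost the same measurement.

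The planned Tukey test would help locate an interaction. This stands in part: it is prespecified, but its comparisons are not listed and its result does not bear on the inference. Reading the overall sign does not close the gap either, because a fall at 0 mg lowers the overall mean.

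Finally, the scenario percentages rest on assumed inputs. That is true, but the rule's indifference to sign and dose does not depend on them.

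**Conclusion.** The point holds as a gap in the decision rule and should be fixed before analysis. The intended direction is plain, so the real weakness is the interaction limb: no pattern is specified and a change confined to placebo cocaine counts. With the sign of the overall mean read sensibly, the null rate is about 5%, but a fall at 0 mg only (logit -1) still passes in about 16-78% of trials. That range depends on the assumed profiles, variances and effect size, and on separate error terms. The 9.75% figure applies only to the literal reading. The design is unaffected. The duplicate primary outcome is a minor matter.

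**What to change.** In section 7, Data Analysis, replace the criterion with:

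1. If the COC-PHEN interaction is significant, declare attenuation only if the planned Tukey comparison shows a significant reduction on PHEN at one or more active COC doses (20, 40, 80 mg) and no active dose is significantly higher.
2. If the interaction is not significant, declare attenuation only if the PHEN main effect is significant with a lower PHEN mean.
3. Test PHEN against subject x PHEN, and the interaction against subject x PHEN x COC.

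Keep 0.05 per test; no alpha split is needed. Optionally, name number of COC doses earned as the single primary outcome, with break point supportive.

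The cost is a few sentences, no new data and some power: from about 72-76% to 65-70% for a reduction at all active doses (logit -0.5), and from about 91-96% to 83-93% for a reduction at 80 mg only (logit -1). Letting a significant, lower main effect suffice even when the interaction is significant would save about 1-2 points of that power, but would raise the fall-at-0-mg figure from 7-10% to 9-26%.

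The proposed rule is not complete protection. Under an assumed mixed effect (logit -1 at 0, 20 and 40 mg, +1 at 80 mg) it still declares attenuation in 6-47% of trials, so the PHEN-placebo difference at every COC dose, 0 mg included, should be reported beside the result.
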